4.3 JUSTIFICATION FOR DOSE

In this trial, the dose of ketamine administered at each infusion (0.5 mg/kg, administered over 40 minutes) is the same dose that is administered in most clinical trials of intravenous ketamine for treatment-resistant depression (TRD), and the same dose that was administered in our two completed clinical trials of intravenous ketamine for chronic PTSD. This dose has shown efficacy and safety for these disorders. Additionally, as requested by the FDA for safety reasons, the maximum dose of ketamine will be 60 mg at each infusion, regardless of participant body weight.

Employing the same dose, frequency, and total number of infusions in this open-label clinical trial of ketamine + WET will allow us to compare study findings to the findings from our completed clinical trial of repeated ketamine infusions for PTSD, which evaluated the efficacy of a repeated course of ketamine infusions, without WET.

4.4 END OF STUDY DEFINITION

A participant is considered to have completed the study if he or she has completed all phases of the study shown in the Schedule of Activities (SoA), Section 1.3. For all participants, the earliest end of study will be the 12-week follow-up assessment. For participants who remain improved at this 12-week assessment, the end of study will be their final follow-up visit (depending on time to loss of this improvement).

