1.3 SCHEDULE OF ACTIVITIES (SOA)

Procedures	Screening	Baseline	Ketamine Infusions	24 hour Follow-Up Visit	Assessment of Response to Ketamine	WET Sessions	Weekly Assessment Until 12 weeks	Monthly Assessment Until Loss-of-Response
	Day - 28 to 0	Visit 1a, Day 1	Visit 1a-9; Days 1, 3, 5, 8, 11, 12	Visit 1b, Day 2	Visit 5, Day 9	Visit 6-12, Days 10, 12, 16, 18, 22	Visits 10, 13-23, Days 12, 19, 26...	Visits 23-26, Days 33...
Informed consent	x							
Demographics	x							
Medical history	x							
SCID-5	x							
CAPS-5	x	x			x		x	x
MADRS	x	x			x		x	x
WTAR	x							
MoCA	x							
IES-R		x	x	x	x			
QIDS-SR		x	x	x	x			
PCL-5	x	x			x		x	x
MOS-5		x					x ¹	
CES		x					x ¹	
PACT		x					x ¹	
CTQ	x							
TLEQ	x							
SDS	x	x		x	x		x	x
HMS			x ²					
PIQ			x ²					
C-SSRS	x	x			x		x	x
CADSS		x	x					
BPRS		x	x					
YMRS		x	x					
Extinction Learning Task	x				x			
CGI	x	x	x	x	x		x	x
Concomitant medication review	x	x	x	x	x		x	x
PRISE	x	x	x	x	x		x	x

Adverse event review and evaluation	x	x	x	x	x	x	x	x
Physical exam (including height and weight)	x							
Vital signs	x		x					
Weight	x		x					
EKG	x							
Routine labs	x							
Plasma ketamine and norketamine levels			x ³					
Urine pregnancy test	x		x					
Urine drug screen (UTOX)	x		x					
Ketamine infusion (0.5 mg/kg)			x					
Written Exposure Therapy (WET)						x		
Complete Case Report Forms (CRFs)	x	x	x	x	x	x	x	x

¹Visit 14 and 23 only

²only at Infusions 1 and 2

³only at Infusion 1

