9.3 POPULATIONS FOR ANALYSES

Analysis datasets will include and Intention-to-treat (ITT) Analysis Dataset (all enrolled patients) and a Per-protocol Analysis Dataset (including only participants who completed the study). Additionally, a Safety Analysis Dataset and descriptive analyses will include all participants in the study.

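### The per-protocol set can lose improvers, but not non-improvers, for missing visits after the week-12 endpoint

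*Combined protocol and SAP*

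**What the plan says.** Section 9.3 (Populations for Analyses) names two sets that matter here. The first is the "Intention-to-treat (ITT) Analysis Dataset (all enrolled patients"). The second, which is the one at issue, is "a Per-protocol Analysis Dataset (including only participants who completed the study"). It gives no other criterion for the per-protocol set.

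The only definition of completion is in section 4.4 (End of Study Definition). A participant has completed the study "if he or she has completed all phases of the study shown in the Schedule of Activities". Two end points follow:

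- The floor, which applies to everyone and is where non-improvers finish: "For all participants, the earliest end of study will be the 12-week follow-up assessment".
- The later point, which applies to improvers alone: "For participants who remain improved at this 12-week assessment, the end of study will be their final follow-up visit". A bracket makes this depend on the time to loss of improvement.

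The Schedule of Activities (section 1.3) has a separate column headed "Monthly Assessment Until Loss-of-Response". Sections 1.1, 4.1 and 9.4.3 restrict that phase to participants improved at week 12. It runs to week 24 or to loss of improvement.

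The primary endpoint is the CAPS-5 change from baseline to 12 weeks after the start of WET (sections 9.1 and 9.4.2). Section 9.4.3 adds the proportion with at least 30% improvement at each time point. Neither 9.4.2 nor 9.4.3 names an analysis set.

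**The concern.** Membership of a set that could be used for a week-12 endpoint is decided by attendance after week 12, and only patients with a good week-12 outcome owe that attendance. This is selection on the outcome. In a per-protocol summary it would remove some of the better results and none of the poorer ones, and it would discard observed primary-endpoint data in a trial of at most 15.

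It would also blur any comparison of the two sets. A difference between them could reflect who kept attending monthly visits rather than who followed the protocol up to the endpoint.

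**Working it through.** **1. The rule applied to two patients.** Both have the full treatment course and a week-12 CAPS-5.

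| | Not improved at week 12 | Improved at week 12, stops attending before week 24 while still improved |
|---|---|---|
| End of study under 4.4 | Week-12 visit | Final monthly visit |
| Completed the study? | Yes | No |
| In per-protocol set (9.3)? | Yes | No |

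An improver who loses improvement, or who reaches week 24, is a completer and stays in. The group exposed is improvers who leave in between. At most three visits are involved (weeks 16, 20 and 24).

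**2. The plan's own precision figure.** Section 9.2 states a 95% half-width of 0.5 SD at n=15.

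- Normal quantile: 1.96/√15 = 0.506 SD, which agrees.
- t quantile, 14 df: 2.145/√15 = 0.554 SD.

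**3. Inputs for an illustration.**

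- SD of change: 11.88/1.13 = 10.5 points, from the difference and effect size of the earlier repeated-infusion trial (section 4.2). That is a between-group contrast at week 2, so it is only a stand-in for the SD of week-12 change.
- Mean change of -12 and baseline of 40: assumed. A 30% fall from 40 is 12 points.
- Meaning of improved: sections 1.1, 4.4 and 9.4.3 put no figure on it for entry to the monthly phase. Two readings are run: a fall of at least 12 points, and any fall.
- Share *f* of improvers leaving after week 12 while still improved: not in the documents, so varied from 10% to 40%. Leavers are taken to be like other improvers.

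**4. Formula.** With *p* the share improved, and m_I and m_N the truncated-normal means of improvers and non-improvers,

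per-protocol mean = [p(1−f)·m_I + (1−p)·m_N] / (1 − p·f), and expected n = 15(1 − p·f).

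- At least 30%: p = 0.50, m_I = -20.4, m_N = -3.6.
- Any decrease: p = 0.87, m_I = -14.5, m_N = 5.2.

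Example at 30%, f = 0.1: (0.45 × -20.4 + 0.50 × -3.6)/0.95 = -11.56.

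| f | ≥30%: mean | shift | n | Any decrease: mean | shift | n |
|---|---|---|---|---|---|---|
| 10% | -11.56 | 0.44 | 14.2 | -11.76 | 0.24 | 13.7 |
| 20% | -11.07 | 0.93 | 13.5 | -11.47 | 0.53 | 12.4 |
| 30% | -10.52 | 1.48 | 12.8 | -11.11 | 0.89 | 11.1 |
| 40% | -9.90 | 2.10 | 12.0 | -10.66 | 1.34 | 9.8 |

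Changing the assumed mean to -8 or -16 leaves the shift at f = 20% between 0.3 and 0.9 points across both readings.

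**5. Scale.** At n=15 and SD 10.5 the half-width is 0.506 × 10.5 = 5.3 points (normal) or 0.554 × 10.5 = 5.8 points (t). The largest shift in the table, 2.1 points, is about 40% of 5.3.

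**6. Responder proportion.** Suppose 10 of 15 improve by at least 30% (67%). Losing one of them after week 12 gives 9/14 (64%). Losing three gives 7/12 (58%), and the normal half-width for the mean goes from 0.506 to 0.566 SD.

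**The case against.** **No planned result is tied to this set.** A reader might infer that the trial's primary result is biased. The documents do not support that. Section 9.3 lists the sets, but no analysis is assigned to the per-protocol one and no comparison of the sets is described. The intention-to-treat set is untouched. The effect arises only if a per-protocol week-12 summary is produced and some improvers leave early. This objection stands and limits the point.

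**The wording of 4.4 could be read otherwise.** Section 9.3 does not cross-refer to 4.4, and the final follow-up visit might mean the last visit attended, which would remove the problem. That reading is weak. The bracket ties the visit to loss of improvement, which points to the planned end, and on the other reading every improver would be a completer whatever they attended. Equally, taking all phases literally would mean that non-improvers never complete. The sentence on the earliest end of study rules that out.

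**Dropout may be low.** A reader might carry over the 25-40% dropout in section 2.1. That figure concerns premature dropout from trauma-focused psychotherapy, and section 2.2 describes attrition from WET as very low. Neither describes monthly assessment after week 12. The rates above are assumptions, and the 10% row is as legitimate as the 40% row.

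**The consequences are modest.** The study is a descriptive pilot without hypothesis tests, and the expected shift runs against the treatment, so no false claim of efficacy follows. This also stands. It does not justify keeping a rule that selects on the outcome when a phrase removes it.

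**Conclusion.** The point holds for the per-protocol set only. Sections 9.3 and 4.4 together state a rule under which an improver with a valid week-12 CAPS-5 can be excluded for leaving, while still improved, before week 24. A non-improver with the same week-12 data cannot be excluded that way.

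The expected direction is towards no effect, provided leavers resemble other improvers. Losing one particular patient with a small improvement could move the mean the other way. Under the stated assumptions the shift is about 0.4 to 2.1 points (improved means at least 30%) or 0.2 to 1.3 points (any decrease), well inside a half-width of 5.3 to 5.8 points. The true size cannot be known from the documents.

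The correction is worthwhile because the defect is in a stated rule and costs almost nothing to remove. The reading that all improvers are at risk goes too far: those who relapse or reach week 24 remain in the set.

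**What to change.** In section 9.3, for all analyses up to week 12, replace the completion criterion with: *completed the study through the 12-week CAPS-5 assessment, regardless of attendance after week 12*. Keep the section 4.4 definition for disposition reporting and for analyses after week 12. Under this wording, leaving after week 12 removes nobody from a week-12 summary, and the shift from this rule is zero.

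Do not add a treatment-exposure criterion, such as a required number of infusions or WET sessions, as part of this change. Section 9.3 has none now, the defect does not require one, and it could itself remove participants with valid week-12 data.

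The cost is one phrase in 9.3, with no new data or visits. The same edit could state which set the week-12 analyses use, since sections 9.4.2 and 9.4.3 leave that open.

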5 STUDY POPULATION

5.1 INCLUSION CRITERIA

INCLUSION

1. Men or women, 18-70 years of age;
2. Participants must have a level of understanding sufficient to agree to all tests and examinations required by the protocol and must sign a written informed consent document;
3. Participants must fulfill DSM-5 criteria for current civilian or combat-related PTSD, based on clinical assessment by a study psychiatrist and on the CAPS-5, and a past-month total CAPS-

5 score \geq 30 at screening – this is done to ensure at least moderate severity and to safeguard against high placebo response rates;

4. Women must be using a medically accepted reliable means of contraception (if using an oral contraceptive medication, they must also be using a barrier contraceptive) or not be of childbearing potential (i.e., surgically sterile, postmenopausal for at least one year);
5. Women of childbearing potential must have a negative pregnancy test at screening and prior to each intravenous infusion;
6. Men who are sexually active with women of childbearing potential must use a medically accepted reliable means of contraception and must agree not to donate sperm for a period of 90 days after receiving the last dose of ketamine;
7. Participants must be able to identify a family member, physician, or friend (i.e. someone who knows them well) who will participate in a Treatment Contract (and e.g. contact the study physician on their behalf in case manic symptoms or suicidal thoughts develop).

5.2 EXCLUSION CRITERIA

EXCLUSION

1. Women who plan to become pregnant, are pregnant or are breast-feeding (because the medical risk of using ketamine during pregnancy and breast-feeding is unknown);
2. Serious, unstable medical illnesses such as hepatic, renal, gastroenterologic, respiratory, cardiovascular, endocrinologic, neurologic, immunologic, or hematologic disease, including gastro-esophageal reflux disease, obstructive sleep apnea, history of difficulty with airway management during previous anesthetics, ischemic heart disease and uncontrolled hypertension, and history of severe head injury;
3. Clinically significant abnormal findings of laboratory parameters, physical examination, or ECG;
4. Renal impairment, as reflected by a BUN >20 mg/dL, and/or creatinin clearance of >1.3 mg/dL;
5. Clinically significant uncorrected hypothyroidism or hyperthyroidism, as indicated by a TSH value 25% above or below the normal range;
6. A Body Mass Index (BMI) >40 ;
7. Hormonal treatment (e.g., estrogen) started in the 3 months prior to the first infusion day;
8. History of a neurodevelopmental disorder (e.g., autism, pervasive developmental disorder) ;
9. History of one or more seizures without a clear and resolved etiology;
10. Lifetime history of bipolar I or II disorder;
11. Presence of psychotic symptoms, or diagnosis of a lifetime psychotic disorder including schizophrenia or schizoaffective disorder;
12. Drug or alcohol use disorder within the preceding 3 months;
13. Previous recreational use of ketamine or PCP on more than one occasion, or any recreational use of ketamine or PCP within the last two years;

14. Previous non-response to clinical or research ketamine or esketamine administration;
15. Current diagnosis of bulimia nervosa or anorexia nervosa;
16. Patients judged clinically to be at serious and imminent suicidal or homicidal risk;
17. SBP >165 and DBP >95 at infusion days – higher BP allowed to account for stress or anxiety;
18. Concurrent treatment with opioid medication, or with long-acting or daytime short-acting benzodiazepines within two weeks of study start;*
19. Current cognitive impairment, as defined by a score <23 on the Montreal Cognitive Assessment (MoCA);
20. Estimated IQ <80;
21. Currently receiving evidence-based psychotherapy for PTSD (e.g., prolonged exposure, cognitive processing therapy);

Note: Concurrent treatment with other psychotropic medications (including a short-acting benzodiazepine at bedtime only) will be permitted, but dose must be stabilized for at least three months before study start.

* Potential participants will not be told to discontinue medication for the purposes of this study if there is any evidence that the medication is clinically beneficial. Further, a study physician will not taper a potential participant off of a medication; rather, this may only be completed by the prescribing physician. This is our policy across all of our studies.

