a. Screening Procedures (see 3.1 Schedule of Activities): Individuals will undergo informed consent procedures and study screening at the clinical site. If the COVID-19 pandemic remains a concern, these procedures will be conducted remotely, via a HIPAA-compliant telehealth platform (e.g., VSee, Doximity, HIPAA-Zoom). After signing the informed consent form, participants will complete a structured diagnostic interview with the SCID-5,⁵¹ the CAPS-5 to determine PTSD symptom severity,⁵⁰ the MADRS to determine depressive symptoms severity,^{52,53} the Wechsler Test of Adult Reading (WTAR),⁵⁴ and the Montreal Cognitive Assessment test (MoCA).⁵⁵ Please see **3.1 Schedule of Activities** for a complete list of scales to be completed by study participants at screening. All subjects will complete forms related to demographics, medical history, concomitant medications and treatment, and self-report measures including the Childhood Trauma Questionnaire (CTQ),⁵⁶ Traumatic Life Events Questionnaire (TLEQ),⁵⁷ PTSD Checklist for DSM-5 (PCL-5),⁵⁸ and Sheehan Disability Scale (SDS).⁵⁹ Participants will also undergo a medical evaluation, including medical history; physical examination by a nurse practitioner; documentation of height, weight and vital signs; comprehensive blood tests; and urinalysis, urine toxicology screen, and urine pregnancy test (in women of childbearing potential). After reviewing all information, the PI or other study psychiatrist will meet with each patient to review their psychiatric and medical history, and current medications and treatment, answer any questions the patient might have,

administer the Columbia Suicide Severity Rating Scale (C-SSRS)⁶⁰ and the CGI-S,⁶¹ document contraceptive use, and verify patient eligibility for the study. If a participant is taking any exclusionary psychotropic medication listed in the exclusion criteria, the prescribing psychiatrist or other prescribing physician must taper the participant off the medication, in consultation with the study PI or other study psychiatrist, if it is determined that the medication is of no clinical benefit to the individual.

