8.2 SAFETY AND OTHER ASSESSMENTS

Participants in this proposed study will provide the following safety data:

- (A) Data related to medical history, physical examination including review of systems, vital signs, ECG, routine laboratory tests (comprehensive metabolic panel, complete blood count, thyroid function testing) needed to determine eligibility and to monitor safety of participants
- (B) Measures to assess for any acute side effects associated with ketamine before and after each infusion; potential longer- lasting side effects will be assessed weekly until resolution.

For laboratory tests, all results will be reviewed by the PI or study-affiliated psychiatrist, and any incidental finding will be conveyed to the subject with provision for additional work-up if needed.

Plasma ketamine and norketamine levels will be assessed via serial blood draws at the first ketamine infusion. Blood will be drawn from a second IV catheter at 30, 60, 90, and 120 minutes from the start of the infusion. Samples will be spun down and aliquoted into plasma samples. These samples will then be transported to Mount Sinai Clinical Laboratory Services (Sinai Labs) for shipment to an external laboratory (LabCorps) for the ketamine and norketamine levels.

The **Patient-Rated Inventory of Side Effects (PRISE)** Adverse Event Visit Checklist⁷¹ is a clinician-administered questionnaire used to qualify side effects by identifying and evaluating the tolerability of each symptom. This scale will be completed before and after each infusion, and at each assessment time point (weekly until 12 weeks, and then monthly up to 24 weeks or until loss of response), by the PI or another study psychiatrist.

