9 STATISTICAL CONSIDERATIONS

9.1 STATISTICAL HYPOTHESES

- Primary Efficacy Endpoint(s):
 - The primary outcome is change in PTSD symptom severity from baseline to 12 weeks from the start of WET measured by the Clinician-Administered PTSD Scale for DSM-5 (CAPS-5) score at 12 weeks from the start of WET minus the CAPS-5 score at baseline. The analysis of the primary endpoint for this pilot study will be descriptive and no formal hypothesis testing will be conducted. The mean change in CAPS-5 score and corresponding 95% confidence interval will be reported.

- Secondary Efficacy Endpoint(s) (Exploratory):

In this early-phase study, analyses of secondary efficacy outcomes will be considered exploratory and hypothesis-generating. Therefore, no formal hypothesis testing will be conducted.

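### Exclusion criterion 4 names creatinine clearance, but its unit and direction fit serum creatinine

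*Combined protocol and SAP*

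**What the plan says.** Section 5.2, item 4, gives two alternative laboratory grounds for excluding a candidate with poor kidney function: "Renal impairment, as reflected by a BUN >20 mg/dL, and/or creatinin clearance of >1.3 mg/dL". The two are joined by and/or, so either one is enough.

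The tests that feed this criterion are described in three places:

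- Section 4.1, under screening procedures, lists "comprehensive blood tests; and urinalysis, urine toxicology screen, and urine pregnancy test".
- Section 8.2 refers to "routine laboratory tests (comprehensive metabolic panel, complete blood count, thyroid function testing) needed to determine eligibility".
- The Schedule of Activities (section 1.3) places routine labs at screening.

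Creatinine is mentioned nowhere else in the documents. There is no timed urine collection, no estimating equation and no limit in mL/min.

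**The concern.** Item 4 is an operative safety rule for a study that gives six ketamine infusions, and it is the only criterion with numeric limits for renal function. If the named measure does not match its unit and sign, the limit cannot be applied as written, and staff must decide for themselves what was meant.

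The wording also matters after screening. Section 7.2 allows withdrawal of a participant who is later found to meet an exclusion criterion. Section 5.4 requires screen-failure details and eligibility criteria to be recorded. Section 10.1.10 treats any noncompliance with the protocol as a deviation. Staff who sensibly apply a serum creatinine limit would be applying a rule that the protocol does not state. Section 10.1.7 says there will be no independent audits, so no outside audit is planned that might notice the mismatch.

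**Working it through.** No sample size, power or alpha figure is involved; section 9.1 says of the primary analysis that "no formal hypothesis testing will be conducted". The check concerns dimension and direction only.

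**Inputs, all from section 5.2, item 4**

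- Named measure: creatinine clearance (spelled without its final e).
- Sign: greater than.
- Value and unit: 1.3 mg/dL.
- Companion limit: "as reflected by a BUN >20 mg/dL".

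**Two checks against each candidate measure**

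| | As written | Clearance | Serum creatinine |
|---|---|---|---|
| Dimension | mg/dL (mass per volume) | volume per time, e.g. mL/min: does not fit | mass per volume: fits |
| Change as kidney function worsens | limit is > | falls, so a limit for impairment would be <: does not fit | rises, so a limit for impairment would be >: fits |

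Clearance fails both checks and serum creatinine passes both. The BUN limit is also a blood concentration in mg/dL with a greater-than sign, so the two halves of item 4 become parallel once the measure is read as serum creatinine.

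**Planned tests.** Sections 4.1 and 8.2 describe blood panels and ordinary urine tests. Neither gives a way to obtain a clearance.

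**Scope.** Section 5.2 sets eight measured-value limits: BUN and creatinine (item 4), TSH (item 5), BMI (item 6), systolic and diastolic pressure (item 17), MoCA (item 19) and estimated IQ (item 20). The creatinine limit is the only one whose named quantity does not fit what is stated about it, so 1 of 8, and 1 of the 2 limits in item 4. Only BUN and creatinine carry a measurement unit, so the unit check has real content for just those two. The tally shows where the error sits and does not measure its consequence.

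**Reading errors ruled out.** The measure, sign, value and unit are all legible, and the text is the current criterion, not an entry in the amendment history.

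**The case against.** The best reply is that this is an editorial slip with no practical effect. Anyone reading a laboratory report will see a creatinine in mg/dL and compare it with 1.3. The BUN limit excludes on its own. Item 2 covers serious, unstable renal illness and item 3 covers clinically significant laboratory abnormalities. The PI or a study psychiatrist reviews all results (section 8.2) and verifies eligibility (section 4.1). Section 5.4 does not say how a criterion must be worded in the screening log, so mislabelled records are a possibility and not a demonstrated outcome.

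Most of this stands as an argument about weight. Unsafe enrolment is unlikely, and nothing in the documents shows that anyone has been or would be misclassified. It does not make the text right. Items 2 and 3 rest on judgement and supply no creatinine limit, and BUN is a separate ground, not a substitute. That the intended meaning can be guessed is a reason to expect little harm, but an eligibility rule should not depend on a guess.

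A second reply is that serum creatinine is itself an inference, since the documents never use the term. That is fair. The intent could have been a clearance or eGFR limit with a less-than sign in mL/min, although that would mean the value, unit and sign were all wrong, and not just one word. This is why the replacement needs medical confirmation.

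**Conclusion.** The concern holds. The creatinine limit in item 4 is wrong in both unit and direction for the measure it names, and no other section corrects it. That much follows from the text alone. The reading as serum creatinine is a strong inference from the unit, the sign, the BUN limit and the planned tests.

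The size is small: one phrase in one criterion, with partial cover from the other limit and from items 2 and 3. The documents give no basis for counting affected candidates, so no count is offered. The sample size of up to 15 (section 9.2) and the primary analysis (section 9.4.2) are unaffected. It should be corrected because the rule cannot be applied literally and the remedy is almost free, not because harm is expected.

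**What to change.** In section 5.2, item 4, replace the creatinine limit with *serum creatinine >1.3 mg/dL*. Leave the number, the unit, the sign and the BUN limit as they are. The medical lead should confirm that this is the intended measure. If a clearance or eGFR limit was meant instead, state it with a less-than sign in mL/min and name the method.

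The change can travel with the next amendment that goes to the IRB and does not need one of its own. Section 10.4 shows that an eligibility cut-off (CAPS-5) has been amended before. No extra test should be needed, on the assumption that the metabolic panel already planned in section 8.2 reports serum creatinine; the protocol does not list the panel's components.
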